The Trial Steering Committee will meet at least three times over the course of the project, and will also be consulted via email and phone as needed. They will review the protocol; oversee the conduct of the study; advise on any ethical issues which may arise including monitoring adverse events and breaches to the protocol; give advice on trial processes such as recruitment; and will monitor the progress of the trial. They will also advise on continuing or stopping the trial. Finally, they will advise on whether to proceed to seek funding for a full trial, and if so, what amendments might be made to the protocol.

Aphasia Advisory Group

This group includes four people with aphasia and one carer. They will meet eight times during the project (four meetings have already been conducted). To date, they have advised on: (1) design of project information, including Participant Information Sheet; (2) recruitment processes; (3) inclusion and exclusion criteria; (4) assessments including choice and presentation of outcome measures; (5) topic guide for indepth interviews; (6) adaptations to the therapy for people with aphasia; (7) building a 'community' around the project e.g. project blog, newsletter; and (8) how to enhance participant experience of taking part in the research (e.g. how best to manage communicating group allocation). The remaining four meetings will focus on: (9) interpreting findings; (10) dissemination; (11) advising on issues that occur in the trial as they arise (e.g. boosting recruitment rates, any ethical concerns); and (12) considering whether or not to proceed to definitive trial.

Protocol amendments since version 1.0

Version and date	Sections	Edit
2.0 (24Aug2017)	Front cover	ClinicalTrials.gov identifier
	4.1	Randomisation: minimisation rather than random permuted blocks
	7.1	Study adopted by North Thames Clinical Research Network

Page 5

Summary of study

Background and Aims

Around one third of people who have a stroke will experience aphasia, a language disability that can affect talking, understanding, reading or writing. The psychosocial impact of aphasia is considerable: those living with chronic aphasia are at risk of social isolation and depression. One potential intervention is Solution Focused Brief Therapy (SFBT). SFBT is an approach to building positive change in a person's life. It builds up a picture of a client's preferred future; encourages a person to notice positive signs of change; explores personal resources, skills and resilience; and acknowledges the impact of the stroke on a person's life and identity.

The current project builds on a small-scale proof-of-concept study that explored SFBT with five people who had mild to moderate aphasia, at least two years post stroke. There were improvements in participants' mood and participation and participants found the therapy highly acceptable.

The main aims of the current project are to assess: [1] the acceptability of SFBT to people with varying presentations of aphasia; and [2] the feasibility of conducting a future definitive trial investigating clinical and cost effectiveness.

Methods

The overall study will last for 38 months (November 2016 to December 2019), and comprise a Development Phase (year 1) and a single-blind, randomised, wait-list controlled, feasibility trial with nested qualitative research comparing SFBT plus usual care to usual care alone (years 2 and 3).

During the Development Phase we will develop the therapy manual and fidelity checking processes, train the clinicians, and finalise the protocol. Phase One has been informed through four workshops with the Aphasia Advisory Group, comprised of four people with aphasia and one carer, who advised on the study protocol and trial documentation. We have also conducted a pilot study with four people who have severe expressive and receptive aphasia where we trialled the assessment and therapy protocol, and explored adapting the therapy for people with severe communication difficulties.

For the feasibility trial (commencing October 2017) we will recruit 32 participants with any severity of aphasia, at least six months post stroke. Potential participants will be identified either through community (e.g. stroke groups) or through two NHS sites. Participants will be randomly assigned to the intervention group or wait-list control group. Both groups will be assessed by a Research Assistant blinded to treatment allocation on psychosocial outcome measures at T1 (baseline, prior to randomisation), T2 (three months

post randomisation) and T3 (six months post randomisation). Participants will also take part in in-depth interviews at T3 exploring their experiences of taking part in the project as well as complete a resource use questionnaire. All participants will receive all usual care, and up to six SFBT sessions spaced over three months delivered by Speech and Language Therapists (SLTs). The intervention group will receive the therapy immediately post randomisation, while the wait-list control group will be offered the intervention after T3. The wait-list control will additionally be reassessed at T4 (nine months post randomisation). We will also interview the trial clinicians, and the Local Collaborators at the two NHS sites.

Results

We will assess the feasibility of recruitment and retention of participants (including proportion who consent; rate of consent; attrition rates), and of treatment fidelity. Descriptive statistics for the clinical outcome measures will be presented, for the entire trial population and by trial arm, at each time point, with means and confidence intervals plotted over time. We will also report the proportion of missing data. As part of the economic evaluation, we will present the relevant costs and health gains by trial arm and assess the completeness of our data collection methods and their acceptability. Qualitative data on acceptability of the intervention and study procedures will be analysed using Framework Analysis.

Clinical Implications

This trial has been designed to assess the acceptability of the intervention for people with varying presentations of aphasia, and the feasibility of conducting a successful definitive trial evaluating clinical and cost effectiveness in the future. Given the high levels of distress and isolation experienced by people living with aphasia, and the current poor evidence base, there is a pressing need to investigate effective psychosocial interventions. SFBT is potentially a relatively brief approach deliverable by SLTs.

Filename: SOFIA Research Protocol v2.docx; Save date: 24Aug2017

Page 7

1. Contents

Abbreviations	2
Study personnel and advisory groups	3
Summary of study	6
1. Contents	8
2. Introduction	10
2.1 Background and rationale	10
2.2 Trial objectives	12
2.3 Trial Design	13

2.1 Background and rationale

Following a stroke around one third of people will experience aphasia¹, a language disability that can affect speaking, understanding, reading or writing. For 15% of stroke survivors aphasia will persist as a chronic life-long condition²; there are around 350,000 people living with aphasia in the UK³. The psychosocial impact of chronic aphasia is considerable. Rates of depression post stroke are estimated at 31%⁴, and for people with aphasia this figure rises to 62-70%⁵. Those with aphasia are disproportionately likely to lose contact with friends^{6,7} and have weaker social networks⁸. People with severe aphasia are particularly at risk of social isolation⁹.

A 2008 Cochrane review on treating depression found no evidence that psychotherapeutic approaches reduced depressive symptoms post stroke¹⁰. Since then, intervention trials have reported positive results for a behavioural intervention¹¹, and motivational interviewing¹² early post stroke. However, both studies included only those with mild aphasia. A recent systematic review of interventions to prevent and treat depression in post-stroke aphasia found limited evidence¹³: the only RCT reporting significant benefit when treating depression in people with aphasia was the Communication and Low Mood (CALM) study¹⁴ where people with aphasia received behavioural activation therapy delivered by assistant psychologists.

The National Clinical Guidelines for Stroke¹⁵ and the NHS Stroke Improvement Programme¹⁶ advocate a stepped care approach offering simpler interventions, such as peer support, for low-level mood problems (level 1), progressing on to more complex interventions requiring input from clinical psychology and psychiatry for persistent and severe mood disorders (level 3). The guidelines stress that 'psychological care for this group [stroke survivors] is as essential as physical rehabilitation' (p5)¹⁶

It is therefore of concern that the recent 2015 Stroke Association's report 'Feeling Overwhelmed' highlighted that two thirds of stroke survivors felt their emotional needs were not as well looked after as their physical needs¹⁷. A recent study explored the views of UK stroke-specialist Speech and Language Therapists (SLTs) through focus groups (n=23)¹⁸ and an on-line survey (n=124)¹⁹. A main theme to emerge was that SLTs considered that people with aphasia, particularly those with more severe aphasia, were often excluded from receiving appropriate psychological support as mental health professionals were perceived as finding it difficult to deliver care due to the communication difficulties, and SLTs, while able to facilitate communication, lacked the necessary support or training to address psychological needs.

Current NICE guidelines suggest that the 'whole multidisciplinary team need to be able to identity psychological issues and know how to manage these issues' (p5)¹⁶, and that level 1 and 2 difficulties (mild/moderate symptoms of depression) may be addressed by non-psychology stroke specialist staff with

support from clinical psychologists. However, there is currently a lack of research evaluating an appropriate level 1/level 2 intervention delivered by SLTs. A psychosocial intervention which could enhance emotional well-being and participation, deliverable by healthcare professionals such as SLTs, could make a valuable contribution to the evidence base. The current study focuses on longer-term psychosocial needs (≥6 months post stroke) as services in this area have been identified as particularly weak²⁰.

Solution Focused Brief Therapy (SFBT). One potential intervention is SFBT. SFBT builds up a picture of a client's preferred future (or how they would like their life to be); encourages a person to notice positive signs of change; and explores personal resources, skills and resilience. It is a relatively brief therapy, typically only three to five sessions²¹. A recent systematic review of the effectiveness of SFBT reviewed 43 controlled outcome studies and found that 74% reported significant positive results, while 23% reported positive trends²². The strongest evidence for its effectiveness was in treating adults with depression. There is a growing evidence base for its effectiveness in managing chronic ill-health, for example, managing fatigue in Crohn's disease²³, and coping with HIV/AIDS²⁴. It has not yet been systematically evaluated for people with stroke and aphasia. However, our group has produced preliminary evidence to guide further work.

Preliminary data. The main trial builds on two preliminary studies: a proof-of-concept and a pilot study.

[1] Proof-of-concept study. This study explored whether it was possible to adapt SFBT for people with post-stroke aphasia. It was funded by the Research Sustainability Fund, City, University of London, and took place September 2013 to May 2014. Five participants took part, recruited via the community (e.g. through stroke groups). The three men and two women were 2-14 years post stroke, with *mild* to *moderate* aphasia. Participants received on average four therapy sessions, and were assessed pre and post therapy. There were improvements in participants' communicative participation (Communicative Participation Item Bank, CPIB²⁶, Cohen's d = 0.81) and mood (General Health Questionnaire-12, GHQ-12²⁷, Cohen's d = 0.79).

Participants also took part in post-therapy in-depth interviews, analysed using Framework Analysis²⁸ by two researchers to minimise bias. A common theme was that participants felt more confident to talk in different situations, for example, on the telephone, ordering drinks in a café, or chatting to others in church. Participants also noted improvements in their mood as well as increased confidence to undertake activities of daily living independently. Some of the mechanisms by which they believed change had occurred were also explored. These included: describing their preferred future in the context of coping with aphasia, being able to identify one's own successful strategies for dealing with difficult emotions or situations, feeling acknowledged, and the process of celebrating achievements. Participants reported finding the therapy approach highly acceptable, although considered four sessions to be insufficient.

[2] Pilot study (Development Phase of current study). We recruited four people (two men, two women) with *severe* expressive and receptive language difficulties (i.e. very limited ability to speak, understand, read or write), as defined by their scores on the Frenchay Aphasia Screening Test²⁹, FAST, (≤7 on both receptive and expressive domains). They were recruited via the community, and were between three and 11 years post stroke, and aged late 40s to early 60s. The aims were to: [1] investigate whether it was feasible to include people with severe communication difficulties in the RCT; and [2] to trial the assessment and therapy protocol. Participants received six therapy sessions spaced over three months, completed before and after outcome measures, and participated in an in-depth interview post therapy (assessments and interview conducted by Research Assistant (RA) not involved with delivery of the therapy). For more information on selected outcome measures please see Section 3.4.2 below.

All participants completed all six therapy sessions. Acceptability was probed during the in-depth interview. All four participants reported finding the therapy valuable, and felt strongly that the approach was suitable for people with severe aphasia. This was picked up in high satisfaction ratings on the Session Rating Scale (SRS)³⁰ (on average 9/10). A common theme was that the therapy enabled them to feel prouder of themselves. They also reported positive changes since starting the therapy (feeling more confident and optimistic, going out more, starting a voluntary job). The primary outcome measure was the Short Warwick Edinburgh Mental Well-being Scale (SWEMWBS)³¹. Pre-therapy mean (SD) was 24.15 (4.99); post-therapy mean (SD) was 28.50 (1.73), Cohen's d was 1.13, indicating a large effect size; there was no missing data, and it was the RA's impression that all participants understood all items. Secondary outcome measures were the Communicative Participation Item Bank (CPIB)²⁶ and the General Health Questionnaire-12 (GHQ-12)²⁷. Again there were no missing items, although the RA reported some participants had difficulty understanding the direction of the response options in the CPIB (see section 3.4.2 for how this will be addressed in the trial). The effect sizes were more modest for the secondary outcome measures (CPIB, Cohen's d = 0.41; GHQ-12, Cohen's d = 0.17). We also trialled the Psychological Outcome Profiles Questionnaire (PSYCHLOPS)³²: this contained significant levels of missing data (over 25%), and the EQ5D5L³³ (no missing data, items found to be comprehensible).

Based on the results of this pilot, we intend to include people with severe aphasia in the feasibility RCT.

2.2 Trial objectives

The main aims of this study are to assess the acceptability of the intervention when delivered to people with varying presentations of aphasia, and the feasibility of conducting a future definitive trial investigating clinical and cost effectiveness.

Primary objectives are to assess:

- [1] Acceptability of the intervention to participants and trial clinicians
- [2] Feasibility of recruitment and retention to the trial
- [3] Acceptability of research procedures and outcome measures
- [4] Feasibility of delivering the intervention by experienced Speech and Language Therapists, following specialist training and with on-going clinical supervision

Secondary objectives are to assess:

- [5] Appropriateness of outcome measures
- [6] Estimate sample size
- [7] Treatment fidelity processes
- [8] Feasibility of documenting usual care and resource use

2.3 Trial Design

The overall study will last for 38 months (November 2016 to December 2019). There will be an initial Development Phase (year 1). In October 2017 we will commence the single blind randomised wait-list controlled feasibility trial, with nested qualitative research, comparing SFBT plus usual care to usual care alone (years 2 and 3). For the feasibility RCT, we will recruit 32 participants with mild to severe aphasia, at least six months post stroke. Participants will be recruited from both the community (e.g. stroke groups) and two NHS sites. They will be randomly assigned to the intervention group or wait-list control group. All participants will receive all usual care. Both groups will be assessed by a Research Assistant blinded to treatment allocation on psychosocial outcome measures at T1 (baseline, prior to randomisation), T2 (three months post randomisation) and T3 (six months post randomisation). The intervention group will receive up to six therapy sessions over three months immediately post randomisation; the wait-list control group will be offered the same intervention after T3, and reassessed three months later at T4.

The intervention will be delivered by Speech and Language Therapists (SLTs) experienced at working with this client group. They will receive a minimum of six days training prior to delivering the intervention. This will include four days 'Foundation' training in SFBT (www.brief.org.uk) followed by a minimum of two days training based at City, University of London, on adapting the approach for this client group and research procedures. They will also receive monthly clinical supervision from an experienced clinician.

The study will include nested qualitative research. We will conduct in-depth interviews with all participants at T3, and with wait-list control at T4. The interviews will be conducted by the CI or an unblinded RA and

will explore participants' experiences of taking part in the study, well-being and participation, as well as experiences of the intervention. We will also conduct in-depth interviews with the trial clinicians to explore how they experienced delivering the therapy to this client group, their perception of the training, supervision and on-going support, and the treatment fidelity processes. Finally, we will interview the two Local Collaborators on recruitment processes.

A further strand of the project will be investigating the feasibility of conducting a full economic evaluation of the relative cost-effectiveness of SFBT plus usual care compared to usual care alone in the definitive trial. We will include the European Quality of Life measure (EQ-5D-5L)³³ as part of the assessment protocol. In addition, at T3 we will ask participants to complete a resource use inventory. This will be a version of the Client Service Receipt Inventory³⁴ (CSRI) adapted for the current project so as to be more relevant and accessible to people with aphasia.

Filename: SOFIA Research Protocol v2.docx; Save date: 24Aug2017

Page 14

2.4 Trial Flowchart

Identification of potential participants

People with post-stroke aphasia identified via: [1] NHS clinical staff from current and past patient records (initial information given about project; for those potentially interested consent sought to pass on contact details to research team); or [2] community (e.g. stroke groups, advertising).

Initial contact, information giving and consent processes

Potential participants interested in the study sent the PIS. CI will then arrange to meet them to discuss the project, and where appropriate, obtain informed consent.

Baseline assessments

T1 assessment visit: Participants complete FAST, DISCS, WEMWBS, GHQ-12, CPIB, EQ-5D-5L (for more information on outcome measures, see Section 3.4)

Randomisation (Time 0): participant data entered into online randomisation system which allocates study group

Intervention

Receive up to six SFBT sessions plus all usual care

Wait-list control

Receive all usual care

3 months post randomisation

T2 assessment visit: Participants complete DISCS, WEMWBS, GHQ-12, CPIB, EQ-5D-5L

6 months post randomisation

T3 assessment visit: Participants complete DISCS, WEMWBS, GHQ-12, CPIB, EQ-5D-5L

T3 interview: Participants take part in in-depth interview (and also complete SRS)

Some participants may receive additional visit to complete adapted CSRI

Wait-list control only

Receive up to six SFBT sessions

9 months post randomisation

T4 assessment visit: Wait-list control only

Participants complete DISCS, WEMWBS, GHQ-

12, CPIB, EQ-5D-5L

T4 interview: In-depth interviews including SRS

3. Methods: Participants, Interventions and Outcomes

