3.3 Intervention

3.3.1 Description

All participants will receive SFBT, either immediately (intervention group), or after a delay of six months (wait-list control group). All participants will also receive all usual care, i.e. all health, social care and voluntary services available to them in their borough. Usual care will be documented as part of the project, using the adapted CSRI at T3.

Solution Focused Brief Therapy

Solution focused brief therapy (SFBT) is an approach to building change. It is distinctive from more problem-based therapy approaches. Instead of exploring the causes of the problem or reducing problem behaviour, SFBT explores how a person would like their life to be, and builds on their resources, resilience, and on what is already working. In SFBT the client is considered expert in their own lives, and the therapist does not seek to offer solutions or strategies. The assumption is that the client will have the resources and skills they need to resolve the problem; the therapist's role is to ask questions and listen in such a way that the client begins to notice their own strengths, and can formulate their own way of moving forwards.

SFBT therapy techniques include:

Eliciting 'best hopes': A first therapy session typically begins with asking a client about their 'best hopes' from the work, thus anchoring the conversation around what is important to the client.

Exploring the 'preferred future': A key aspect of the approach is to enable a person to visualise how they would like their life to be, thus shifting perspective from their problems to visualising an alternative future where their 'best hopes' are realised. In describing their preferred future, a client is typically facilitated to provide as much concrete, observable, small-scale detail as possible, with an emphasis on describing positive features i.e. what is wanted, rather than the absence of negative features.

Scaling questions: A variety of scaling questions are used flexibly within SFBT. The most commonly used scale is where ten represents 'best hopes realised', and zero represents the opposite. Clients are invited to

place themselves somewhere on this scale. The scaling question can be used to elicit instances of success, strengths, resources and resilience, for example, through exploring how the client is not at a zero. It can also be used to explore progress towards a client's preferred future.

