3.4 Outcomes

3.4.1 Primary and secondary endpoints

As a feasibility study the main endpoints relate to the feasibility objectives listed in Section 2.2 above. When the purpose of a study is to investigate the feasibility of proceeding to a definitive trial, it is recommended that researchers specify on what criteria they will base this decision ⁴³. We outline formal pre-specified criteria to guide the decision as to whether to proceed to a future definitive trial: the extent to which these thresholds have been met will be considered in conjunction with qualitative evidence. The pre-specified criteria are based on published trials investigating complex behavioural interventions with people with aphasia ^{14,44} or stroke ^{11,12}: reported recruitment, retention and compliance rates have informed what we consider to be realistic progression criteria.

Primary endpoints:

[1] Acceptability of the intervention to participants and trial clinicians: based on in-depth interviews with participants (at T3, T4) and trial clinicians (at end of study); trial clinicians' therapy records (e.g. whether progress was made towards best hopes; acceptability; what challenges were encountered); rates of compliance; scores on the Session Rating Scale.

Pre-specified criteria:

• Proportion of participants who are compliant (attend at least two sessions of SFBT): at least 80%

[2] Feasibility of recruitment and retention to the trial: based on proportion who are eligible of records screened (for those participants identified via NHS prospectively); proportion told about study by direct care team who consent to be contacted by CI; proportion who consent of those who are eligible; rate of participants randomised each month; attrition rates (overall, by stage, and by study arm).

Pre-specified criteria:

Proportion of eligible participants who consent: at least 60%

Proportion of participants who are followed up at 6 months post randomisation: at least 70%

[3] Acceptability of research procedures and outcome measures: based on rates of missing data, drop-out rates, length of assessment sessions, and participant interviews.

Pre-specified criteria:

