3.5 Duration of the study and participant timeline

Study duration: the study is funded for 38 months (November 2016 to December 2019). The initial Development Phase will run for 11 months, from November 2016 to September 2017. The feasibility RCT will run for 29 months, from October 2017 to December 2019. Enrolment to RCT will last for 13 months (October 2017 to November 2018).

Duration of participant involvement: participants allocated to the intervention arm will be in the study for approximately 6 months from recruitment; participants allocated to the wait-list control condition for approximately 9 months. Below is a detailed description of the participant timeline during the feasibility RCT.

Participant Timeline

Purpose	Person responsible	Time	Forms/ Measures	Description	Arm of trial
Identification	SLT (via NHS); Self-identified (via community)	10 minutes	Initial information one-page sheet	Potential participants identified, and asked permission for their contact details to be passed to research team.	All
Information giving	Cl	15 minutes	Full Participant Information Sheet	CI to send potential participant PIS at least 24 hours prior to visiting.	All
Information giving and consent	CI	60 minutes	PIS; consent form	CI to visit potential participant (location of participant's choice) and discuss the project, going through the PIS in detail. Written consent to be obtained.	All
T1 Assessment and baseline profiling	RA	50 minutes	FAST; WEMWBS; DISCS; GHQ-12; CPIB; EQ-5D-5L; case history	Outcome measures completed in interview format. FAST at baseline only.	All
Randomisation	CI	10 minutes		Letter, visit or phone call (participant preference) to inform them of group allocation.	All
Intervention	Trial clinicians	6 visits (each visit about 60 minutes)		SFBT therapy sessions	Intervention Arm
T2 Assessment (3 months post randomisation)	Blinded RA	30 minutes	WEMWBS; DISCS; GHQ-12; CPIB; EQ-5D-5L	Face-to-face visit to conduct assessments	All
T3 Assessment (6 months post randomisation)	Blinded RA	30 minutes	WEMWBS; DISCS; GHQ-12; CPIB; EQ-5D-5L	Face-to-face visit to conduct assessments	All
T3 in-depth interview	Unblinded RA or Cl	60 minutes	topic guide; SRS	Face-to-face interview	All
T3 resource use questionnaire	CI	20 minutes	Adapted CSRI	Optional additional visit	All
Intervention	Trial clinicians	6 visits (each visit about 60 minutes)		SFBT therapy sessions	Wait-list control arm

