3.6 Sample size

For the feasibility RCT, we will recruit 32 participants in total, 16 participants allocated to each arm of the project. If around 15% are lost to follow up¹⁴, we anticipate that around 28 will be followed up at 6 months. This sample is adequate to inform the parameters of a larger trial, such as recruitment rates, consent rates, completion rates, acceptability, and potentially effect size of outcome measures⁵².

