5.3.1 Quantitative analysis

For all descriptive statistics outlined below, we will calculate appropriate 95% confidence intervals.

Study Objective One: acceptability of the intervention. We will provide descriptive statistics for the proportion of participants who comply with the intervention; and the proportion of participants who evaluate the overall intervention (Item 4 of the SRS) at 6/10 or higher, indicating a favourable opinion.

Study Objective Two: feasibility of recruitment and retention. We will analyse: [1] the proportion who are eligible of records screened (for those participants recruited prospectively via NHS only); [2] proportion who consent to have their details passed on to CI; [3] the number who are eligible per month; [4] proportion who consent of those eligible (number who consent/number eligible); [5] rate of consent per month; and [6] rate of recruitment (participants randomised) per month. We will also analyse [7] the frequency and [8] the proportion of participants who withdraw or are lost to follow up overall, by study arm, and by stage including those who do so before and after randomisation will be presented. Finally, we will analyse [9] the baseline characteristics of those missing follow up and those with complete follow up. Secondary analysis of items [3] to [9] will be conducted to see if the rates/ proportions vary according to style of recruitment (i.e. NHS prospective; NHS retrospective; community).

Study Objectives Three and Eight: acceptability of research procedures and outcome measures; feasibility of documenting usual care and resource use. We will analyse the proportion of missing data for each assessment overall and by treatment group (including FAST, SRS, all clinical outcome measures, and the EQ-5D-5L and adapted CSRI). Length of time to conduct T1-T4 visits will also be documented. The adapted

CSRI includes an added Likert item on acceptability; and also an item on time taken to complete. Descriptive statistics for this will be presented.

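### The Session Rating Scale is scheduled at T3 for both arms, although the wait-list arm has had no therapy to rate by then

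*Protocol*

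**What the plan says.** **Schedule.** The flowchart (Protocol Section 2.4) describes the six-month visit as "T3 interview: Participants take part in in-depth interview (and also complete SRS"; the block reserved for the wait-list arm begins only below that point. In the Section 3.5 timeline, the T3 interview row gives its materials as "topic guide; SRS" and its arm as *All*. Section 3.4.2 places the SRS at the T3 and T4 interviews without mentioning arm, and Section 2.3 has every participant interviewed at T3 and the wait-list arm again at T4.

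**Timing of therapy.** Section 3.3.1 states: "All participants will receive SFBT, either immediately (intervention group), or after a delay of six months (wait-list control group". Sections 2.3 and 2.4 agree that wait-list therapy follows T3.

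**Use of the ratings.** Section 3.4.1 names SRS scores as one source for the first primary endpoint, acceptability of the intervention. For Objective One, Section 5.3.1 reports "the proportion of participants who evaluate the overall intervention (Item 4 of the SRS) at 6/10 or higher". For Objectives Three and Eight it says: "We will analyse the proportion of missing data for each assessment overall and by treatment group (including FAST, SRS" and further measures.

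**The concern.** Before T3 a wait-list participant has had no trial session and no trial therapist, so the form has no subject. The arm label does not look like loose wording. The same timeline limits other rows to one arm, and the flowchart marks the later steps as wait-list only. Nothing in the protocol exempts the wait-list arm from the T3 form.

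Two planned results are exposed:

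- The item 4 proportion has neither a time point nor a denominator, although the wait-list arm is scheduled for two ratings, one of them before therapy.
- SRS missingness is reported by treatment group. Forms left blank because they do not apply would look like poorer completion in the wait-list arm, and acceptability of the measures is what that analysis is meant to judge.

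**Working it through.** **Inputs**

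- Section 3.6: "we will recruit 32 participants in total, 16 participants allocated to each arm of the project".
- Section 3.6, on attrition: "If around 15% are lost to follow up", with around 28 expected at six months.
- Sections 2.4 and 3.5: SRS at T3 in both arms, and at T4 in the wait-list arm.
- Sections 2.3, 2.4 and 3.3.1: wait-list SFBT after T3.

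**The plan's own figure.** 32 × (1 − 0.15) = 27.2, against the stated figure of around 28. This agrees to within rounding (28 of 32 is a loss of 12.5%).

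**Count of scheduled ratings, full sample**

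- Intervention T3: 16. Wait-list T3: 16. Wait-list T4: 16. Total: 48.
- Ratings with no therapy behind them: the 16 wait-list ratings at T3.
- Share of all ratings: 16/48 = 33.3%. Share of T3 ratings: 16/32 = 50%. Share of the wait-list arm's ratings: 16/32 = 50%.

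**Sensitivity to attrition**

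| Scenario | Intervention T3 | Wait-list T3 | Wait-list T4 | Share with nothing to rate |
|---|---|---|---|---|
| No loss | 16 | 16 | 16 | 16/48 = 33.3% |
| 28 retained, no later loss | 14 | 14 | 14 | 14/42 = 33.3% |
| 70% retained (expected counts) | 11.2 | 11.2 | 11.2 | 11.2/33.6 = 33.3% |
| 28 retained, wait-list 12 at T4 (assumed) | 14 | 14 | 12 | 14/40 = 35.0% |
| 28 retained, wait-list 10 at T4 (assumed) | 14 | 14 | 10 | 14/38 = 36.8% |

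The share is one third under equal loss and slightly more if the wait-list arm loses people between T3 and T4.

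**If the forms are blank and counted as missing.** Suppose every treated person completes the form. Missingness is then 0/16 = 0% in the intervention arm, 16/32 = 50% in the wait-list arm and 16/48 = 33.3% overall. With 10% genuine missingness among valid ratings (assumed), it is 10% in the intervention arm, (16 + 1.6)/32 = 55% in the wait-list arm and (16 + 3.2)/48 = 40% overall. The excess comes from the schedule alone.

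**If the forms are filled in.** The scores of untreated people cannot be predicted, so the effect on item 4 has no single size. As an illustration only, take 80% favourable among the 32 valid ratings and pool all 48. The result lies between 25.6/48 = 53.3% (no untreated rating favourable) and (25.6 + 16)/48 = 86.7% (all favourable). Section 5.3.1 counts participants and does not specify such pooling, so this shows only that the result depends on a choice left open.

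**After the fix.** Scheduled ratings are 16 + 16 = 32 (28 if 28 people are retained through their own post-therapy rating). None lacks therapy to rate, and structural missingness falls from 33.3% to 0%.

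**The case against.** The strongest reply is that nobody would carry this out literally. The arm column may describe the interview visit rather than each form used at it. Section 2.3 says the T3 interviews cover experience of the intervention, which cannot apply to untreated people either. The interviewer is the CI or an unblinded research assistant, who knows that a wait-list participant has had no therapist. The item 4 statistic concerns people who evaluate the intervention, which suggests recipients. If the form is skipped and each person contributes one post-therapy rating, the acceptability proportion is unaffected. That last point stands and limits the consequence. It does not remove the instruction: the protocol assigns the form to both arms, and a skipped form would still count as missing unless it is declared not applicable. An SAP could set a denominator, but who receives which form at which visit is set by the protocol.

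A reader might infer more than the documents support:

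- *Favourable ratings cannot exceed 50%.* This treats T3 as the only time point. Section 5.3.1 does not say so, and the wait-list arm can give valid ratings at T4, so 32/32 is possible.
- *The 15% missing-data criterion would fail.* Section 3.4.1 applies it to people with mild to moderate receptive aphasia, under research procedures and outcome measures. Section 3.4.2 lists the SRS among profiling and covariate measures, so it is unclear whether the criterion covers it.
- *The compliance criterion is also unsettled.* It reads "Proportion of participants who are compliant (attend at least two sessions of SFBT): at least 80" percent. The pass marks of 13/16 and 26/32 are both 81.25%, the same 80% rule rounded up.
- *The arms rate therapy after different intervals.* That follows from a wait-list design with a six-month endpoint, and no between-arm comparison of SRS scores is planned.

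**Conclusion.** The schedule error holds. As written, 16 of 48 SRS ratings (33%, and half of those at T3) are asked of people who have had no trial therapy. The count rests on 16 per arm, SRS use as shown in Sections 2.4 and 3.5, and no wait-list SFBT before T3; it is stable under equal attrition.

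The consequence is conditional. Completed forms would be meaningless scores that can enter the item 4 proportion, and blank forms would be structural missingness in one arm. Which of these happens, if either, depends on handling that the protocol does not fix.

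It would be wrong to conclude that the trial's acceptability result is distorted as a matter of course, or that a go/no-go threshold turns on this. Item 4 has no progression threshold, and neither the WEMWBS comparison nor the numerical progression criteria are shown to be affected. This is a correction worth making, confined to one instrument.

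**What to change.** In Sections 2.4, 3.4.2 and 3.5, schedule the SRS at T3 for the intervention arm only and at T4 for the wait-list arm only. The T3 interview itself can stay for both arms. In Section 5.3.1, base the item 4 proportion and SRS missingness on one post-therapy rating per participant who attended at least one session.

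The cost is a few lines of text in the flowchart, the measures list, the timeline and two analysis sentences. No valid rating is lost, and up to 16 form completions are spared for people with aphasia.
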